Three way interaction among gabapentin, duloxetine, and donepezil in patients with diabetic neuropathy

Investigators: [name].; [name].; [name]., [name]., [name], R.N.

Hypothesis: Based on laboratory studies and our understanding of their mechanism of action, there will be a profound positive interaction between two oral drugs approved for the treatment of neuropathic pain (gabapentin and duloxetine) and an oral drug approved for treatment of dementia (donepezil) to treat patients with chronic pain.

Background: We have recently demonstrated that peripheral nerve injury in rats, which

results in hypersensitivity to mechanical stimuli and presumably chronic pain, also results in increased capacity for analgesia. Specifically, nerve injury induces sprouting of noradrenergic fibers in the dorsal horn of the spinal cord, accompanied by changes in α 2-adrenoceptor function and development of a spinal α 2-adrenoceptor - cholinergic circuit. These changes likely underlie the increased potency and efficacy of intrathecal clonidine observed in animals and humans with chronic compared to acute pain, but may have considerably wider therapeutic implications. For example, commonly used, oral drugs for the treatment of neuropathic pain, gabapentin and antidepressants, may depend in part on this noradrenergic plasticity for their efficacy. A summary of the hypothesized

[figure not shown]

Figure : This study will test whether 1. Gabapentin produces analgesia after nerve injury by a spinal noradrenergic mechanism, and its effects are enhanced by 2. the norepinephrine transporter inhibitor, duloxetine, and 3. the cholinesterase inhibitor, donepezil

sites and mechanisms of action of drugs to be studied in this application is shown in the adjacent figure.

Version 8 October 19, 2010 Page 1 of 11 We are currently examining in the laboratory the mechanisms which lead to sprouting of noradrenergic fibers in the spinal cord in models of chronic pain as well as the mechanisms that lead to a novel noradrenergic – cholinergic circuit in the spinal cord. In addition to examining the circumstances which generate this increased capacity for analgesia and the mechanisms by which they occur, we will test in this protocol whether approved and experimental treatments for neuropathic pain exploit this increased capacity.

This study is in patients with neuropathic pain, and will culminate in a quantitative description of interactions between activators of descending noradrenergic activity, norepinephrine transporter inhibitors, and cholinesterase inhibitors to exploit this unique plasticity of analgesia in chronic pain states. We focus not only on mechanistic hypotheses in the laboratory studies, but also on practical applications, using clinically approved drugs, including gabapentin (Neurontin®) to activate noradrenergic activity, duloxetine (Cymbalta®) to inhibit the norepinephrine transporter, and donepezil (Aricept®), approved for the treatment of Alzheimer's dementia, but not previously tested to treat neuropathic pain, to inhibit cholinesterase. Each of these drugs may act by mechanisms in addition to those involved in descending noradrenergic inhibition, but we hypothesize that the therapeutic strength of their combination relies heavily on this cascade engendered by noradrenergic sprouting and altered α 2-adrenoceptor function. The proposed studies will provide critical tests of this hypothesis and critical information to guide more effective clinical therapy of neuropathic pain.

Protocol

Inclusion Criteria:

A total of sixty-six patients with diabetic neuropathic pain will be recruited from the Department of Neurology at Wake Forest University School of Medicine, surrounding Piedmont Triad community and we will also have a second site at the Cleveland Clinic Foundation in Cleveland Ohio. Patients with predominant neuropathic pain following back surgery will also be enrolled. Approximately 46

Version VI February 10, 2009 Page 2 of 11 subjects will be enrolled at WFUHS and 20 will be enrolled from the Pain Clinic at the Cleveland Clinic. Wake Forest University Health Sciences will be the coordinating center. [name], will be the PI for the Cleveland Clinic site. Subjects from the Cleveland Clinic will follow the same protocol as the WFUHS subjects.

1. Diagnosis of diabetic neuropathy

2. Age 18-80

3. Willing to temporarily discontinue gabapentin or monoamine reuptake inhibitors upon entry into the study

Subjects will be able to continue their other prescribed medications maintaining a stable dose.

4. Diagnosis of failed back syndrome.

Exclusion Criteria:

- 1. Pregnant women or women of child-bearing potential not willing to practice a reliable form of birth control as specified in the informed consent
- 2. Allergy to duloxetine, gabapentin, donepezil or other piperidine derivatives (including fentanyl, alfentanil, sulfentanil, remifentanyl, demerol, tramadol, loperamide, diphenoxylate, betaprodine, alphaprodine, ethoprodine, anileridine, diminodine, MPTP, loradine, fexofenadine
- 3. Unstable medical conditions including cardiac, pulmonary, renal or hepatic diseases that, in the opinion of the investigator, would preclude patients from finishing the trial
- 4. Any person with pending litigation
- 5. A history of major psychosis requiring hospitalization within the last three years
- 6. Non-English speaking, illiterate, unable to comprehend consent
- 7. Lack of contact information
- 8. Known hypersensitivity to duloxetine or any of the inactive ingredients

Version VI February 10, 2009 Page 3 of 11

- Treatment with a monoamine oxidase inhibitor (MAOI) within 14 days of randomization or potential need to use an MAOI during the study or within 5 days of discontinuation of study drug
- 10. Uncontrolled narrow-angle glaucoma
- 11. Currently being treatment with thioridazine (Mellaril)
- 12. Patients taking opioids will be excluded if they are taking a dosage that exceeds an equivalent of 30 mg of morphine per day
- 13. Patients taking more than one regular (not rescue) medication for pain
- 14. Patients taking donepezil for dementia
- 15. Patients with a baseline pain score less than 2 (0-10 scale) or greater than 8 (0-10) will be excluded

Drug Administration (basis of randomization):

Following a two week baseline period, patients will be seen in The General Clinical Research Center (GCRC) at Wake Forest University Baptist Medical Center and data from the PDA device downloaded and checked for compliance. Patients will be randomized, using a balanced and double blind design, to receive either duloxetine, 30 mg bid, donepezil, 5 mg qd, both duloxetine 30 mg and donepezil 2.5 mg qd, or placebo for the next 12 weeks. All randomizations will include study medication to be taken twice a day to maintain the blinding for all groups. Placebo pills will be provided in addition to the study medications for group 1 and group 4 will take two placebo pills. At the end of 6 weeks, patients will return to The General Clinical Research Center and data from the PDA downloaded and checked for compliance. All patients will then receive gabapentin, 400 mg three times daily, titrated twice a week by telephone interview with the research nurse or investigator for three weeks up to a maximum of 3200 mg per day. Titration up or down will be determined by presence and severity of side effects and efficacy of analgesic treatment, using a standardized interview. Subjects will then be maintained on this gabapentin dose for 3 more weeks. At the end of this 6 week period of gabapentin administration, patients will return to The General Clinical Research Center and data from the PDA downloaded and checked for compliance. Their experimental treatment (placebo, duloxetine, donepezil, or combination) will then be Version VI February 10, 2009 Page 4 of 11

stopped for two weeks, with daily PDA entry and titration of gabapentin twice weekly by standardized telephone interview.

Experimental Design:

	Visit		Visit						Visit						Visit		Visit
	1		2						3						4		5
Informed	Х																
Consent																	
Urine	Х																
Pregnancy Test																	
Pain	Х																
Questionnaires																	
Physical Exam	Х																
PDA	Х																
Instructions																	
PDA Download			Х						Х						Х		Х
Randomization			Х														
Blinded Study Med			Х	Х	Х	Х	Х	Х	Х	Х	Х	Х	Х	Х	Х		
Gabapentin									Х	Х	Х	Х	Х	Х	Х	Х	Х

Primary Outcome Measures:

Pain intensity measurements will be recorded twice daily, in the a.m. and p.m. using McGill short form pain questionnaire displayed on the personal digital assistant (PDA). The SF-MPQ is comprised of 15 descriptors (11 sensory; 4 affective) with an intensity scale from 0-3 (3 being the most severe), present pain intensity (PPI), and Visual Analog Pain Scale (VAS). The VAS will serve as the study's primary outcome measure.

Statistical Analyses:

All data will be analyzed using the most recent version of SPSS (SPSS Inc., Chicago, IL). Prior to performing analyses related to the aims and hypotheses, descriptive statistics will be computed to examine if assumptions needed for parametric analysis are met. Our previous studies of daily pain reports from neuropathic pain Version VI February 10, 2009 Page 6 of 11 patients (1) have indicated that such reports can be expected to be approximately normally distributed. If parametric assumptions are not met, standard transformations will be used to make the data more normal. An intent-to-treat analysis will be undertaken for all participants that receive at least one study dose (with last observation carried forward for drop-outs) with no attempts being made to impute missing data. A two-tailed probability value of .05 will be used for statistical significance criterion in all analyses.

To examine differences in the primary outcome of twice-daily pain reports as a function of "medication group" and "study phase", a Linear Mixed Model will be used. Subjects will be treated as a random variable, with the average of the daily pain reports nested within subject. A first-order autoregressive error term will be used to account for the repeated measures within subjects. Although all observations will be used to specify the model, only the observations from the last week (the optimal therapeutic dose) of each study phase ("baseline", "study med", and "gabapentin") will be used to evaluate the hypothesis. In essence, this allows changes in the dependent variable of pain reports to be modeled by two ANCOVAs (controlling for baseline). Group (placebo, duloxetine, donepezil, and duloxetine + donepezil) differences in pain reports will be evaluated separately at end of treatment alone and at end of treatment with gabapentin portions of the study. A significant group effect will indicate that mean self-reported pain scores differed significantly by treatment arm assignment during that phase of the study._ If a main effect is found, post hoc analyses will be conducted to indicate the location of the differences and to index the degree of change exhibited by study group.

In addition to the primary analyses, we will examine pre-post changes in disability measures and psychometric measures, global assessments of change, and medication use. Each of these outcomes will be examined using General Linear Models (GLM), examining for differences in group either at one time period or as a function of study phase, as appropriate. Further, because the study design will result in a time-series of pain reports for each subject, we will fully utilize the available data by creating individualized interrupted time-series analysis models for each subject. Within each phase, increases in dose will be modeled as a gradual, permanent intervention. We will utilize ARIMA models (2) to account for the unique data structure that our design results

Version VI February 10, 2009 Page 7 of 11 (i.e., diurnal variation in AM and PM reports). These analyses will better elucidate the nature of individual differences in the medication responses and identify the dose-response function for each medication condition.

Statistical Power Considerations:

For the proposed study all power calculations are based on the primary analysis of the primary outcome measure (daily pain reports). ANCOVA analyses were chosen to evaluate the primary outcome as they have repeatedly been shown to be the most powerful technique for these comparisons (3). Our previous diary studies examining novel agents on neuropathic pain (1) have demonstrated that high levels of visual analog pain reporting are common, M = 60.5, and that substantial variation is often observed, even within day-to-day reporting, SD = 14. Nevertheless, first-order autocorrelation among observations is often observed, r = .20. For the present study, we are preparing for a considerable placebo effect of 20%. Because of the novel nature of the agents being studied, we would like to detect differences as small as 5% between the active treatment and placebo groups (i.e., a 25% reduction in pain from baseline). Using Cohen's formulation for ANCOVA (6) (f = .25, r = .50 between phases) with adjustment (4) for the calculation of our repeated assessment of each study phase (7 observations contributed by each subject at each phase, first-order autocorrelation = .20), we estimate that an n = 15 for each medication group (15 x 4 = N = 60) will provide power = .80. It is of note that the proposed sample size indicates the number of participants that take at least one dose of the study drugs (i.e., recruitment will end when N = 60 participants have taken at least one dose of study medication). Further, the 16 week trial, with two observations per day provides a sufficient number of observations ($n \sim 224$ observations/subject) to incorporate the interrupted time-series analysis strategy for the secondary analyses (5).

Adverse Events/Side Effects:

Version VI February 10, 2009 Page 8 of 11 The most common side effects of duloxetine observed in diabetic peripheral neuropathy groups include but are not limited to nausea, excessive drowsiness, dizziness, constipation, dry mouth, excessive sweating, decreased appetite and weakness.

The most common side effects of gabapentin are dizziness, excessive drowsiness, peripheral edema, nausea, dry mouth, constipation and ataxia. Other side effects include tiredness, flu syndrome, double or blurred vision, shakiness, and abnormal thinking.

Common side effects of donepezil include (but are not limited to) nausea, diarrhea, vomiting, weight loss, if experienced usually subside within a few days. . Adverse events that were also reported during clinical trials conducted with donepezil include: headache, pain in various locations, accident, fatigue, fainting, loss of appetite, bruising, muscle cramps, arthritis, insomnia, dizziness, depression, abnormal dreams, sleepiness, and frequent urination.

Additional warnings per package insert of donepezil are:

Anesthesia: ARICEPT[®], as a cholinesterase inhibitor, is likely to exaggerate succinylcholine-type muscle relaxation during anesthesia.

Cardiovascular Conditions: Because of their pharmacological action, cholinesterase inhibitors may have vagotonic effects on the sinoatrial and atrioventricular nodes. This effect may manifest as bradycardia or heart block in patients both with and without known underlying cardiac conduction abnormalities. Syncopal episodes have been reported in association with the use of ARICEPT[®].

Gastrointestinal Conditions: Through their primary action, cholinesterase inhibitors may be expected to increase gastric acid secretion due to increased cholinergic activity. Therefore, patients should be monitored closely for symptoms of active or occult gastrointestinal bleeding, especially those at increased risk for developing ulcers, e.g., those with a history of ulcer disease or those receiving concurrent nonsteroidal antiinflammatory drugs (NSAIDS). Clinical studies of ARICEPT[®] have shown no increase, relative to placebo, in the incidence of either peptic ulcer disease or gastrointestinal bleeding.

Version VI February 10, 2009 Page 9 of 11 ARICEPT[®], as a predictable consequence of its pharmacological properties, has been shown to produce diarrhea, nausea and vomiting. These effects, when they occur, appear more frequently with the 10 mg/day dose than with the 5 mg/day dose. In most cases, these effects have been mild and transient, sometimes lasting one to three weeks, and have resolved during continued use of ARICEPT[®].

Genitourinary: Although not observed in clinical trials of ARICEPT[®], cholinomimetics may cause bladder outflow obstruction.

Neurological Conditions: Seizures: Cholinomimetics are believed to have some potential to cause generalized convulsions. However, seizure activity also may be a manifestation of Alzheimer's Disease.

Pulmonary Conditions: Because of their cholinomimetic actions, cholinesterase inhibitors should be prescribed with care to patients with a history of asthma or obstructive pulmonary disease.

Risks:

Risks of the medications are described above. There is an overlap in side effects between gabapentin and duloxetine regarding sedation. As such, one could see enhanced sedation with this mixture. This should be minimized in the current study, since gabapentin is being titrated according to side effects. Additionally, there is a risk of temporary exacerbation of chronic pain during the washout period or if drugs are ineffective. Please note that we are studying patients who are failing current analgesic therapy, and this study may benefit these patients by providing a novel combination of medications otherwise not used. Data will be stored in a secure location. Additionally, the personal digital assistants (PDA) will hold no personal identification information.

Data Safety Monitoring Plan

Data will be continually monitored by the study coordinator and reported to the principal investigator who will review the data and all adverse events after each subject is studied. Serious and unexpected adverse events will be reported to the IRB within 24 hours of discovery.

Version VI February 10, 2009 Page 10 of 11 3-way interaction [name]. Anesthesiology

References:

- 3. Senn S. Repeated measures in clinical trials: analysis using mean summary statistics and its implication for design. Stat Med 1994;13:197-8.
- Vickers AJ. How many repeated measures in repeated measures designs?
 Statistical issues for comparative trials. BMC Med Res Meth 2003;3:1-9.
- Cohen JC. Statistical Power Analysis for the Behavioral Sciences, second edition. Lawrence Erlbaum Associates: Hillsdale, NJ. 1988.

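### The primary analysis averages AM and PM pain by day with no time-of-day term and no rule for one-report days, so unequal one-sided missing entries could bias the arm comparison

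*Combined protocol and SAP*

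**What the plan says.** Under Primary Outcome Measures: "Pain intensity measurements will be recorded twice daily, in the a.m. and p.m", and "The VAS will serve as the study's primary outcome measure". Under Statistical Analyses, subjects are random, "with the average of the daily pain reports nested within subject", with a first-order autoregressive error. The hypothesis tests use "only the observations from the last week (the optimal therapeutic dose) of each study phase". Statistical Power Considerations confirms that the unit is the day: "7 observations contributed by each subject at each phase, first-order autocorrelation = .20".

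On missing data, Statistical Analyses carries the last observation forward for drop-outs, "with no attempts being made to impute missing data". It does not say how a day with a single report is scored. The same section names "diurnal variation in AM and PM reports" as a feature of the data, but only as a reason for the secondary single-patient ARIMA models. The primary model has no time-of-day term.

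The PDA is downloaded and checked for compliance at the visits in weeks 2, 8, 14 and 16 (Experimental Design). No completeness threshold or AM/PM requirement is stated.

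**The concern.** On a day with both reports, averaging balances morning and evening. On a day with one report, the average is simply that report. If mornings and evenings differ in level, such a day is shifted by half the gap. If one arm loses more evenings (or mornings) than another, the shift enters the arm difference. A model fitted to daily averages cannot remove it, because time of day is no longer in its data. Baseline adjustment does not help if the pattern of gaps starts on treatment.

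Arms could plausibly differ in this way. Adverse Events/Side Effects lists excessive drowsiness for duloxetine, and both insomnia and sleepiness for donepezil; placebo patients take neither drug. For the second comparison, "The most common side effects of gabapentin are dizziness, excessive drowsiness, peripheral edema". Gabapentin goes to every arm, but its dose is titrated individually and so may differ by arm. Because the diary is downloaded at the visit that closes each phase, gaps in the decisive week come to light after that week has passed.

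At stake is the estimate at the end of randomized treatment alone and at the end of treatment with gabapentin, measured against a small target difference.

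**Working it through.** **The plan's own figure.** Stated power is .80 with 15 per group. A noncentral F with 3 and 55 df and noncentrality N x f² reproduces it under one reading. Treat r = .20 as the correlation between every pair of the 7 days, and f = .25 as already adjusted for baseline. The variance factor is (1 + 6 x 0.20)/7 = 0.314, f becomes 0.25/√0.314 = 0.446, and power is 0.808. This confirms that the day is the planned unit. The present point does not change the figure.

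**Inputs from the documents.** Mean VAS 60.5, and a target of 5% between active and placebo. Taken as 5% of 60.5, the target is 0.05 x 60.5 = 3.025 points.

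**Inputs assumed, because the documents do not give them.** D is the systematic AM-PM gap, 5 to 15 points. Δ is the between-arm difference in the net share of one-sided days (PM-only minus AM-only), 10% to 20%.

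**Formula if the available report is used.** Let AM reports average μ - D/2 and PM reports μ + D/2. A two-report day averages μ, an AM-only day μ - D/2, and a PM-only day μ + D/2. The arm mean is then μ + (D/2) x (share PM-only - share AM-only), so the bias in the arm difference is (D/2) x Δ.

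| D | Δ = 10% | Δ = 20% |
|---|---|---|
| 5 | 0.25 (8% of target) | 0.50 (17%) |
| 10 | 0.50 (17%) | 1.0 (33%) |
| 15 | 0.75 (25%) | 1.5 (50%) |

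Half the target is reached only when D x Δ is about 3.0, for example a 10-point gap with a 30% excess.

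**Simulation under no drug effect** (two arms of 15, 7 days, 4,000 runs, between-patient and within-report SD both set at 10). AM missing was 30% in one arm and 10% in the other.

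| D | Formula | Daily average of available reports | AM and PM averaged separately, equal weight | Difference |
|---|---|---|---|---|
| 5 | 0.50 | 0.63 | 0.13 | 0.50 |
| 10 | 1.0 | 1.04 | 0.05 | 0.99 |
| 14 | 1.4 | 1.37 | -0.04 | 1.40 |

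Both scores come from the same simulated data, so their difference isolates the artefact, and it matches the formula. With equal missingness (10% or 20% in both arms) the bias was -0.06 to 0.06, that is, zero within simulation error.

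**Effect on the test.** Rejection under no effect was 5.6% to 6.2% at 30% versus 10% missing, and 5.7% to 8.6% at 40% versus 10%. With equal AM/PM weighting it was 4.9% to 5.6%. With between-patient SD 10 and within-report SD 14, a week's mean of 14 readings has variance 100 + 196/14 = 114. The standard error of a two-arm difference is √(2 x 114/15) = 3.9. A bias of 0.25 to 1.5 is therefore 0.06 to 0.38 standard errors.

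**If the raw readings are pooled instead.** The plan also calls the outcome twice-daily. If single readings were modelled without an AM/PM term and a share m of PM entries were missing, the arm mean would shift by D x m/[2(2 - m)]. With D = 10 and m = 25% versus 5%, that is 10 x 0.25/3.5 - 10 x 0.05/3.9 = 0.71 - 0.13 = about 0.6 points. The problem shrinks but remains.

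**The case against.** A reader might infer that the plan prescribes averaging whichever report exists and that its arm comparison is therefore biased. The documents do not support that. The rule for one-report days is not in the text. Setting such a day to missing is also compatible with it, and every analysed day would then hold one AM and one PM score, so the artefact would not arise. Bias further needs both a systematic AM-PM gap and a net one-sided difference between arms. The plan's mention of diurnal variation gives neither size nor direction.

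Nor do the documents link drowsiness to missed entries, or to one time of day; if mornings and evenings are lost equally, the effects cancel. Gabapentin alone does not separate the arms, and nobody has started it at the first comparison. The figure of 50% of target combines the largest assumed gap with the largest assumed excess, and the inflation of type I error is small.

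All of this stands, and it makes the point conditional. It does not remove it. The plan does not say that one-report days are dropped, and dropping them would discard usable readings. Pooling raw readings without an AM/PM term leaves part of the bias. A further objection also stands: averaging AM and PM separately is undefined for a patient with no AM or no PM entries in the week, so that method needs a fallback.

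**Conclusion.** The point holds as a conditional one. The primary unit is a daily average, gaps within the diary are not imputed, no time-of-day term is fitted, and the plan itself expects AM and PM to differ. If the available report scores a one-report day, the arm difference could be off by 0.25 to 1.5 points (8% to 50% of a target of about 3.0). This rests on an assumed gap of 5 to 15 points and an assumed excess of 10% to 20%, and it is zero with equal missingness. The consequence is mainly a distorted estimate; at moderate assumed values the false-positive rate rises only to about 6%. The drowsiness mechanism is plausible, not shown. The change is worth making because it uses data already collected and protects the comparison whether or not the arms differ in missingness.

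**What to change.** Fit the primary mixed model to the twice-daily VAS readings with AM/PM as a fixed effect, and specify the AR(1) structure for twice-daily data (up to 14 ordered readings per last week instead of 7 daily values). This form also covers a patient with only AM or only PM entries, by borrowing the gap estimated from the other patients.

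Alternatively, for each patient and each last week, including the baseline week, average the AM scores and the PM scores separately and take the mean of the two. Use the AM/PM-adjusted model for patients with no AM or no PM entries that week.

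Under either option, report AM and PM completeness by arm for each last week.

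No new data and no change in sample size are needed. The separate-average option costs a sentence or two and a few lines of code. The model option costs somewhat more, because the error structure and the 7-observation description must be restated for twice-daily data.

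### The title, hypothesis and aim concern interaction among three drugs, but the planned tests compare four arm means within each phase, and no interaction contrast in pain is specified

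*Combined protocol and SAP*

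**What the plan says.** The title is "Three way interaction among gabapentin, duloxetine, and donepezil in patients with diabetic neuropathy". The Hypothesis predicts a strong positive interaction of the three drugs. The Background figure legend says of gabapentin that "its effects are enhanced by 2. the norepinephrine transporter inhibitor, duloxetine, and 3. the cholinesterase inhibitor, donepezil", and the Background adds that the study "will culminate in a quantitative description of interactions between activators of descending noradrenergic activity, norepinephrine transporter inhibitors, and cholinesterase inhibitors".

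The Statistical Analyses section fits a mixed model to pain by medication group and study phase. It then reduces the evaluation of the hypothesis to two baseline-adjusted ANCOVAs on last-week data: group "differences in pain reports will be evaluated separately at end of treatment alone and at end of treatment with gabapentin portions of the study". The meaning of a positive result is stated: "A significant group effect will indicate that mean self-reported pain scores differed significantly by treatment arm assignment during that phase of the study". A follow-up step comes only when that test is positive, and its purpose is described as follows: "post hoc analyses will be conducted to indicate the location of the differences and to index the degree of change exhibited by study group". General linear models by group or phase are planned for disability, psychometric, global-change and medication-use outcomes, not for pain. Pain reports are also used for "creating individualized interrupted time-series analysis models for each subject", aimed at individual responses and a dose-response for each condition.

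Statistical Power Considerations sizes the trial for the ANCOVA group comparison only.

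Two design facts matter here. Everyone receives open-label gabapentin from the end of week 8, titrated on side effects and efficacy. And Drug Administration and Experimental Design both give the single arms as duloxetine 30 mg bid and donepezil 5 mg qd, and the combination as duloxetine 30 mg with donepezil 2.5 mg qd. Drug Administration also says that all arms take study medication twice a day.

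**The concern.** A difference among four arm means is not an interaction. Two drugs that each work and simply add will separate the arms, and so will two drugs that block one another. Gabapentin is not randomized, so its interaction with a randomized drug has to be read from how arm differences change between week 8 and week 14, or from the gabapentin dose reached. The two phases are instead evaluated separately. A drug worth 3 points at week 8 still differs from placebo by 3 points at week 14 if gabapentin merely adds.

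The risk is that a significant group effect is reported under an interaction title and read as support for the hypothesis, while the quantity in the title is never estimated. Contrasts chosen after the data are seen would carry much less weight than ones named now.

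**Working it through.** **Inputs from the plan.** 15 per arm, 4 arms, two-sided .05, SD 14, 7 observations per phase, autocorrelation .20, f = .25, r = .50 between phases, mean pain 60.5, target difference 5% (taken as .05 × 60.5 = 3.0 points). Residual df = 60 − 4 − 1 = 55.

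**SD of a weekly mean (not given, so assumed).**
- Exchangeable correlation: 14 × √((1 + 6 × .20)/7) = 7.85. With the baseline-covariate gain √(1 − .50²) = .866, it is 6.80.
- First-order autoregressive: variance factor .2015, so 14 × √.2015 = 6.28, or 5.44 with the covariate gain.
- No gain from averaging: 14. If SD 14 is a within-person figure, the between-person SD could exceed 14.

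**Reproducing the plan's power.** f = .25 corresponds to an SD of means of .25 × 14 = 3.5. At SD 7.85, λ = 60 × 3.5²/7.85² = 11.9, and the noncentral F (3, 55 df) gives .81, against .80 stated. The other SDs, 6.80, 6.28, 5.44 and 14, give .91, .95, .99 and .32. I use 6.80 to 7.85 as the central range because 7.85 reproduces the plan.

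**What the group test shows.** Patterns are points of pain reduction for placebo / duloxetine / donepezil / combination, with equal component doses. Interaction = combination − duloxetine − donepezil + placebo. Ranges run from SD 7.85 to SD 6.80.

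| Pattern | Interaction | Group test significant | Combination beats both single arms (unadjusted) |
|---|---|---|---|
| 0/4.95/4.95/9.9 | 0 | .81–.91 | .24–.34 |
| 0/0/0/8 | +8 | .80–.91 | .67–.81 |
| 0/8/8/8 | −8 | .80–.91 | .005 |
| 0/8/8/16 | 0 | above .99 | .67–.81 |

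The first row is f = .25 arranged additively: 0/D/D/2D has SD of means D/√2, so D = 3.5 × √2 = 4.95. Rows two and three have the same sum of squares about their mean (48), hence the same probability with opposite signs of interaction. Over SD 5.44 to 14, the first row's group-test probability runs from .99 to .32, and rows two and three run together from .99 to .31.

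**What the post hoc step shows.** That the combination beats both single arms separates synergy (row two) from antagonism (row three), and partly from the additive pattern at the plan's f (row one). It does not separate row two from row four: .67 to .81 in both, or .40 to .58 in both with Tukey adjustment. Single arm versus placebo helps there: about .05 in row two against .78 to .89 in row four. None of this is an estimate of interaction. The 2x2 contrast is: it is significantly positive in .49 to .61 of trials under row two and .025 under row four.

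**Precision of the contrasts.**
- 2x2 contrast: SE = SD × √(4/15) = 3.51 to 4.05. CI half-width = 2.004 × SE = 7.0 to 8.1 points. Detectable at .80 power = 2.852 × SE = 10.0 to 11.6 points. Power for 3 points is .11 to .13.
- Week 8 to week 14 change, assuming r = .50 also holds between those weeks: SD of change = SD × √(2 × (1 − .50)) = SD. At SD 7.85 the three-way contrast detects 11.6 points. Each arm-versus-placebo change has SE 7.85 × √(2/15) = 2.87 and detects 8.2 points.

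**The case against.** The strongest reply is that the plan is not blind to interaction. Study phase is in the model, the post hoc step covers all arm differences, medication use is analyzed by group or phase, and the randomized drug is withdrawn in weeks 15–16 while gabapentin continues. Several parts of this stand.

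- A reader might infer that the post hoc results can never tell synergy from additivity. The documents and the arithmetic do not support that. The equality holds for 0/0/0/8 against 0/8/8/16, and the latter assumes 8 points per drug where the plan targets about 3. At the plan's f the additive pattern gives only .24 to .34, and single-arm-versus-placebo tests help to separate even the equal pair.
- A reader might infer that a gabapentin interaction can show only as an arm-by-phase difference in pain. Because titration depends partly on efficacy, it can also show as a difference in gabapentin dose. The medication-use models may cover that dose, but they do not say so.
- If the combination is read as half of each single-arm dose, comparing it with the single arms does bear on super-additivity. That comparison falls within the post hoc step, but it is not named and is run only after a main effect.

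What does not stand is that any of these estimates the interaction in pain. The phases are evaluated separately, the post hoc contrasts are unspecified, the per-subject time-series models specify no between-arm comparison, and the withdrawal weeks are not among the phases used to evaluate the hypothesis.

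**Conclusion.** The concern holds as a mismatch between the stated question and the specified analysis: no contrast for non-additivity, arm-by-phase change or three-way interaction in pain is planned, and a significant group test is not evidence of interaction. The central probabilities (.81 to .91 under exact additivity at f = .25; .80 to .91 for either sign of an 8-point interaction) assume equal component doses, 15 per arm and a weekly-mean SD of 6.80 to 7.85. The true SD could be lower, or above 14. That the group test cannot show the sign of an interaction does not depend on the SD.

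A reader might go further and conclude that the trial's primary comparison is invalid. The documents do not support that: the comparison of arms is valid as planned, and the trial is sized for it. This is therefore a cheap improvement that should be made, not a fault that defeats the trial.

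**What to change.** First reconcile the combination-arm and single-arm dose text in Drug Administration and Experimental Design, because it decides which contrast addresses additivity. Then pre-specify, from the planned mixed model, with 95% CIs and not conditional on the group test:

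1. If component doses are equal: combination − duloxetine − donepezil + placebo at the end of each phase.
2. Under the same condition: the week 8 to week 14 change in that contrast, as the three-way estimate.
3. In either case: the week 8 to week 14 change in each active arm versus placebo, with week-14 gabapentin dose by arm.

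If component doses differ, state that (1) and (2) do not test additivity, and compare the combination with each single arm. Read superiority over the better one as super-additivity only if the combination's two dose fractions, each relative to its single arm, sum to no more than 1. That reading assumes dose additivity with monotone dose-response curves.

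Name one contrast as the primary interaction estimate and the rest as supportive. With equal doses, (2) matches the title, while (1) at week 8 is free of gabapentin titration. Keep the group test as the efficacy test and do not report it as evidence of interaction. If interaction will not be estimated, restate the title, hypothesis and aim as a comparison of arms.

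The cost is plan wording and a few contrast statements. The pain data are already to be collected, and gabapentin dose is known from titration. The drawback is the low precision shown above, which wording cannot remove. Between-phase contrasts also mix in longer exposure to the randomized drugs and differing gabapentin doses. The plan should say both.
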